4.1 Substudies

There will be no substudies.

5 STUDY ENROLLMENT AND WITHDRAWAL

5.1 Subject Inclusion Criteria

Once the HSCs on the Navajo reservation are selected for the study, the HSC will be randomized to the two intervention groups. Subject inclusion criteria include:

- A) Children ages 3-6 years at the time of enrollment in the Navajo reservation HSCs and having a primary caregiver (preferably parent, or the child's legal guardian as documented by the HSC, but another caregiver such as an aunt or grandmother will not be excluded if he or she is the primary caregiver for the child). A parent or legal guardian must be available to give consent for the child to participate in the study. (Note: multiple children from the same family will not be excluded, provided each child is enrolled in the Navajo Head Start Program.)
- B) American Indian, as defined by the tribe, or children of other races/ethnic groups who are in the HS classes on the Navajo reservation (the numbers in this latter group are expected to be very small); and
- C) Parent/caregiver able to read, understand, and sign a consent form for his or her own participation, and willing and able to follow study procedures and instructions.

5.2 Subject Exclusion Criteria

A child will be excluded if he/she has any of these conditions:

- A) Allergy to any of the components of the FV (for children attending HSCs in Group 1)
- B) Ulcerative gingivitis, stomatitis or other conditions resulting in chronically disrupted or irritated oral mucosa (for children attending HSCs in Group 1)
- C) Any other conditions or findings that, in the opinion of the investigator, would interfere with or preclude participation in the study in either Group 1 or Group 2.

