7 STUDY SCHEDULE

7.1 Screening

Children and parents will be screened for entry into the study according to inclusion/exclusion criteria at the time of enrollment.

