7.2 Enrollment

Once the HS programs that will participate in the two treatment arms have been identified, study staff will travel to each participating site and host sessions for teachers, staff and parents to explain the program and begin obtaining informed consent from parents. Upon obtaining informed consent from a parent/legal guardian, the child will be enrolled in the study, along with his/her parent/primary caregiver, who also will provide informed consent. A baseline oral health screening will be completed, along with the ACASI survey completed by the parents/caregivers regarding demographic information about the children, health history, and the parents'/caregivers' dental knowledge, attitudes, and behaviors. Toothbrushes and toothpaste will be given, enough for each family member in the household.

Prior to the varnish dates, under normal and usual conditions, notices will be sent home with children notifying parents of the upcoming varnish date(s) for the COHS intervention group. The notice will state the date(s) that the COHS will be administering FV in the HS classroom.

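### Exclusion criteria A and B apply only in Group 1 centres and after randomisation, so the two enrolled populations are defined slightly differently

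*Combined protocol and SAP*

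**What the plan says.** Section 5.2 lists three exclusion criteria. Criterion A is "Allergy to any of the components of the FV (for children attending HSCs in Group 1"; criterion B is "Ulcerative gingivitis, stomatitis or other conditions resulting in chronically disrupted or irritated oral mucosa (for children attending HSCs in Group 1". Criterion C, which rests on the investigator's opinion, is worded for both arms: it covers conditions that would "interfere with or preclude participation in the study in either Group 1 or Group 2". The contrast with C shows that the limit on A and B is intended.

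The order of events is set out in three places. Section 5.1: "Once the HSCs on the Navajo reservation are selected for the study, the HSC will be randomized to the two intervention groups". Section 7.2, on recruitment: "Once the HS programs that will participate in the two treatment arms have been identified, study staff will travel to each participating site", where they hold information sessions and obtain consent. Section 7.1: "Children and parents will be screened for entry into the study according to inclusion/exclusion criteria at the time of enrollment". Section 5.3.2 adds that the interventions are not masked; among those in contact with the children, only the hygienists who score caries are to be blinded.

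**The concern.** In a cluster trial that recruits after randomisation, the arms stay comparable only if children enter both by the same rule. Here they do not. A child with a varnish-component allergy or chronically irritated mucosa is turned away in a Group 1 centre, while the same child in a Group 2 centre is enrolled, followed and analysed. The staff applying the rule can know the arm.

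Criterion B describes an oral condition. If it goes with faster caries progression, the filter removes some high-increment children from the intervention arm only and makes the intervention look better than it is. The protocol text makes no provision for recording A or B status in Group 2 and plans no sensitivity analysis without such children. As written, the imbalance could be neither measured nor corrected afterwards.

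**Working it through.** The plan gives no figure for this point, so there is none to reproduce. The check has two parts: the logic of the text, and the size under stated assumptions.

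**Logic.** Sections 5.1, 7.2 and 7.1 together give this sequence: centre selected, centre randomised, arm identified, staff visit, consent, child screened against section 5.2. Criteria A and B act at the last step and in one arm only. The following safeguards do not reverse this:
- Section 10.2, item 8 (intention to treat) keeps in follow-up those subjects who drop out. It cannot restore a child who was never enrolled.
- Section 5.3.4 asks a child who reacts to varnish to stay in the evaluation without the treatment. It too acts only after enrolment.
- Section 10.4 describes baseline as a customary covariate. This would absorb part of a difference in baseline dmfs, but not necessarily a difference in later increment.

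**Inputs from section 10.2.** Usual-care mean dmfs 24; SD 24; 40% reduction; 520 children per arm (taken as given); 70% retention; class size 20; intraclass correlation 0.045; type I error 0.05 (sidedness not stated, two-sided assumed).

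**Assumed inputs, not in the documents.** p, the share of children meeting A or B; D, their mean excess increment in surfaces over other children.

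**Shift.** Let other children have mean increment μ under usual care. Without a treatment effect, Group 1 has mean μ and Group 2 has mean (1 − p)μ + p(μ + D) = μ + pD. The bias is therefore pD.
- Low: 0.01 × 5 = 0.05 surfaces.
- High: 0.02 × 10 = 0.20 surfaces.
- Children concerned per 520: 520 × 0.01 = 5.2 to 520 × 0.02 = 10.4.

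**Against the planned effect.** 0.40 × 24 = 9.6 surfaces. 0.05/9.6 = 0.5%; 0.20/9.6 = 2.1%.

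**Against sampling error.** Retained per arm: 0.70 × 520 = 364. Retained per class: 0.70 × 20 = 14. Design effect: 1 + 13 × 0.045 = 1.585. Standard error of the difference: 24 × √(2 × 1.585/364) = 2.24 surfaces. 0.05/2.24 = 2.2%; 0.20/2.24 = 8.9%.

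**Type I error**, with b = pD: 1 − Φ(1.96 − b/2.24) + Φ(−1.96 − b/2.24). The last two rows are deliberately extreme.

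| p | D | Shift | Share of 9.6 | Type I error |
|---|---|---|---|---|
| 1% | 5 | 0.05 | 0.5% | 0.050 |
| 2% | 10 | 0.20 | 2.1% | 0.051 |
| 2% | 24 | 0.48 | 5.0% | 0.055 |
| 5% | 24 | 1.20 | 12.5% | 0.083 |

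If D = 0, the shift is zero whatever p is.

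**The case against.** The strongest reply accepts the asymmetry and disputes its consequences. Most of it stands.

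A reader might infer that the bias is known to favour the intervention. The documents do not support that. Nothing in them links varnish allergy or irritated mucosa to caries increment, and for allergy no reason is apparent. The outcome is change from baseline, and a child with heavy disease at entry has fewer sound surfaces left to convert, so D could be zero or negative.

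A reader might also infer that the intention-to-treat analysis is broken. Item 8 of section 10.2 concerns enrolled children who drop out. What happens here is differential eligibility at recruitment, a separate and milder problem.

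A third tempting reading is that the data to apply A and B in Group 2 are already collected. Section 7.2 does say "A baseline oral health screening will be completed" and mentions a parent survey with health history. It names no allergy item, however, and section 8.1 describes the screening as collecting dmfs, with no mention of mucosal findings. Section 7.2 also describes both steps after the child is enrolled, whereas section 7.1 applies eligibility at enrolment. The screening procedure in Appendix D is not in the text available, so it may say more.

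Finally, identical wording does not guarantee identical application when recruiters know the arm. This is true, and it favours a fixed checklist item. It is no reason to keep criteria that differ by design.

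**Conclusion.** The point holds as a minor design flaw. Two criteria are specific to one arm and act after the arms are known, and no other section repairs this. Comparability is slightly weakened. Any bias would favour the intervention only if affected children have higher increments, which is plausible for criterion B and unsupported for criterion A.

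Under the main assumptions (1% to 2% of children, 5 to 10 surfaces) the shift is small beside both the planned effect and the standard error, and would not by itself change the trial's conclusion. Both assumed inputs come from outside the documents. The standard error uses the SD of 24 that section 10.2 gives for dmfs itself; a smaller SD for the change score would raise the ratio in proportion. The case for acting rests on the low cost of removing the asymmetry, not on a large expected bias.

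**What to change.** Make eligibility for the analysed population the same in both arms. There are two ways to do this.

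1. Delete the two Group 1 qualifiers in section 5.2 and add an A/B checklist item at enrolment in Group 2, completed in the same way as in Group 1. The shift pD is then zero by design if the criteria are applied alike. Cost: one checklist item, and a handful of Group 2 children not enrolled (about 5 to 10 of 520 under the assumed prevalence).
2. Keep the criteria, record A/B status in both arms at enrolment (including children screened out in Group 1), and pre-specify in section 10.4 a sensitivity analysis that leaves out such children in both arms. Cost: the checklist item and one extra analysis. No further child is excluded, and the trial learns the actual prevalence. The primary comparison keeps the asymmetry, but its effect becomes visible.

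Neither option changes the rule on who may receive varnish.

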5.3 Treatment Assignment Procedures

5.3.1 Randomization Procedures

A list of Navajo HSCs and the population sizes will be provided to the University of Colorado Center for Native Oral Health Research (CNOHR) by the Navajo Nation Head Start Program. The HSCs will be stratified by number of HS classes (1 vs. 2-3) and by Navajo

agency (there are 5 agencies), and then the randomization of the HSCs into intervention vs. control will be done within those strata. This will be done to ensure approximately equal sample sizes in the intervention and control groups, and approximately an equal number of intervention and control participants within each Navajo agency. A program will be developed to do the randomization within each stratum. Random numbers will be generated, and if the random number ends with the digit 0-4, the HSC will be assigned to the control arm and if the random number ends with the digit 5-9, the HSC will be assigned to the intervention arm.

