4 STUDY DESIGN

This is a multicenter, Phase IV, cluster randomized trial to determine whether an intensive intervention of COHS's administering FV (offered 4x a year) and OHP for 2 years in an AI population of children ages 3-6 years in HSCs on the Navajo Reservation vs. usual oral health care made available by the IHS dental providers will reduce the dmfs measure in the children. A cluster randomized design was chosen to reduce the potential for contamination between the 2 intervention groups.

There are approximately 96 HSC classrooms in the NN (based on 2011-2012 school year). We will stratify HSCs on the basis of population size, and randomly assign the HSC classrooms to the 2 arms of the study within the strata. This will make the number of children in each of the 2 arms of the study approximately equal.

The intensive intervention group will have the specially-trained COHS administer FV to the children 4x a year and provide OHP to the parents/caregivers and to the children in the HS classrooms, for 2 years. The other randomized group will have usual oral health care made available by the IHS Dental providers or other community providers.

Enrollment of HSCs will be done over a period of 6 months (in each year, year 1 and year 2). Upon parental consent of the child and parent/primary caregiver consent for her/himself, the HS children from each HSC classroom will be enrolled in the study. Each consented child will participate in the study for up to 3 years. A baseline assessment of the dmfs measure for each child will be done (objective 3.1.1.3 and 3.1.2.1/ outcome 3.2.1 and 3.2.2.1), and a baseline assessment of the dental knowledge, attitudes, and behaviors of the parents/caregivers (objectives 3.1.2.2 and 3.1.2.3/ outcome 3.2.2.2 and 3.2.2.3). The interventions will be administered for 2 years in the Head Start classrooms. The number of interventions a participating child receives will vary with the length of time that the child attends the Head Start class. Annual assessments of the dmfs measure for the children and the dental knowledge, attitudes, and behaviors of the parents/caregivers will be made for 3 years. The 3rd annual assessment is included to determine changes in the outcome measures for up to 18 months after the FV and OHP have ended, to assess the longer term effects of the intervention.

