10.4 Final Analysis Plan

The primary outcome measure will be the difference between groups 1 and 2 on the changes in mean dmfs between baseline and 2-year and 3-year follow-up. Descriptive statistics will be examined first to yield important information about the most appropriate analysis strategies. If the change scores for dmfs are not normally distributed, a log transformation can be made, or a non-parametric test can be used. Longitudinal methods of analysis will be used to examine these repeated, correlated observations within subjects over time.^{32, 33} Other models such as negative binomial regression, mixture models such as ZIP and ZINB will be considered.

Exploratory analyses will first be done to evaluate the trends in the data to determine the most appropriate mean and covariance structures for the data. Graphical displays will be used to assess the mean structure for modeling fixed effects, including scatter plots of the response variable versus time, plots of individual subject profiles, plots of mean profiles, and smooth curve fits to the data. Simple plots of individual subject profiles (dmfs over time) can be very revealing and show whether there is heteroscedasticity in the data (fanning of the curves with time).

Linear mixed models will be used because they can incorporate both fixed and random (subject-specific) effects and permit different covariance structures. A typical example (“random regression”) allows each subject an individual time trend, and treatment effects may cause differences in slope over time. The within-subjects autocorrelation is assumed to be due to these individual trends, on top of which is superimposed independent measurement errors. When analyzing randomized trials, it is assumed that the responses are the values that occur after randomization, because they are influenced by treatment. Thus, it is customary in such trials to consider the baseline value as a covariate, rather than as a response variable. The randomization of subjects in groups or clusters (i.e., HSCs) can also be accounted for in the mixed model with a random effect for group.

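### Class number and agency stratify the randomisation but are not named in the primary model, and baseline dmfs is not firmly committed as a covariate

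*Combined protocol and SAP*

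**What the plan says.** **Randomisation.** Section 5.3.1 sets two stratification factors. The first is class number: "The HSCs will be stratified by number of HS classes (1 vs. 2-3"). The second is "agency (there are 5 agencies), and then the randomization of the HSCs into intervention vs. control will be done within those strata". Crossed, they give 10 strata. The section's stated aim is similar arm sizes overall and within each agency. Within a stratum, "if the random number ends with the digit 0-4, the HSC will be assigned to the control arm", and digits 5-9 send it to the intervention arm. No blocking or other restriction is described.

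**Design description.** Section 4 says "We will stratify HSCs on the basis of population size, and randomly assign the HSC classrooms to the 2 arms". The Protocol Summary likewise mentions population size only. Neither mentions agency.

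**Analysis.** Section 10.4 opens with "The primary outcome measure will be the difference between groups 1 and 2 on the changes in mean dmfs between baseline" and the 2-year and 3-year follow-up. It commits to linear mixed models and then remarks that "it is customary in such trials to consider the baseline value as a covariate". Clustering by center "can also be accounted for in the mixed model with a random effect for group". The mean structure is to be settled after the covariance structure. The secondary hierarchical models add sociodemographics and mediators. Class number, agency and strata appear nowhere in 10.4.

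**The concern.** Factors important enough to stratify on would normally be in the primary model, named in advance. They are known at randomisation, so adjusting for them cannot be suspected of data-driven selection. Here the link is missing, and the role of baseline dmfs can be read in two ways: through a change score, or as a covariate in a model for the follow-up values.

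Two things are at stake. First, the final-digit rule lets the arms differ by agency or center size by chance, and a model without those terms does nothing to correct the estimate. Second, any between-center variation that agency and center size explain stays in the error term. The open choice on baseline also leaves the precision of the primary comparison, and to some degree its value, to be decided after the data have been explored.

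**Working it through.** **Inputs from section 10.2.** Control mean 24, SD 24, 40% reduction (9.6 surfaces), alpha 0.05 (two-sided, inferred from the alternative hypothesis), power 0.80, 20 children per class, ICC 0.045, 70% retention, 26 classrooms and 520 children per arm. Retained children per classroom: 20 × 0.70 = 14.

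**Assumed, because the documents do not give them.** q, the share of between-cluster variance explained by the strata; r, the correlation of baseline with follow-up dmfs.

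**1. The plan's own sample size.** 2 × (24 × (1.960 + 0.842) / 9.6)² = 98.1 per arm. Design effect 1 + 19 × 0.045 = 1.855. Then 98.1 × 1.855 / 0.70 = 260 per arm, or 13 classrooms. The stated 520 per arm and 26 classrooms are twice that. The Appendix B table is not in the text, so this cannot be resolved here. It is a separate matter, but it sets the context for power. With 520 × 0.70 = 364 retained per arm, power for the 40% effect is 97.7% (design effect 1.855) or 99.0% (1 + 13 × 0.045 = 1.585).

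**2. Does the allocation rule enforce balance?** Each center gets an independent draw with probability 1/2. For 52 units, P(26/26) = 0.11 and P(30/22 or worse) = 0.33. As an illustration, assume 10 units in an agency. P(7-3 or worse) = 2 × (120 + 45 + 10 + 1) / 1024 = 0.34, and the chance that at least one of five such agencies is that uneven is 1 − 0.656⁵ = 0.88. Stratifying under this rule does not secure balance.

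**3. Precision from the strata.** The variance of a cluster mean is proportional to ICC + (1 − ICC)/m. At m = 14 this is 0.045 + 0.955/14 = 0.1132, and the between-cluster part is 0.045/0.1132 = 0.397. Variance factor with strata: 1 − 0.397q. For power I used the noncentral t, with a noncentrality of 2.857 giving 80% on 50 cluster df. I divided this by the square root of the variance factor and used 45 df (4 for agency, 1 for class number).

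| q | variance factor, m = 14 | power, m = 14 | power, m = 20 |
|---|---|---|---|
| 0 | 1.000 | 79.8% | 79.8% |
| 0.10 | 0.960 | 81.4% | 81.7% |
| 0.25 | 0.901 | 83.8% | 84.7% |
| 0.50 | 0.801 | 87.8% | 89.5% |

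With 13 clusters per arm (24 df, less 5) and m = 14, the same four values are 79.1, 80.7, 83.1 and 87.2%. The cost when the strata explain nothing is then about 0.9 points instead of 0.2.

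**4. Precision from baseline.** Relative to the variance of a follow-up value, with equal variances at both times, a change score has factor 2(1 − r) and covariate adjustment 1 − r². Their ratio is (1 + r)/2.

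| r | covariate / change score | variance saved |
|---|---|---|
| 0.5 | 0.75 | 25% |
| 0.7 | 0.85 | 15% |
| 0.8 | 0.90 | 10% |
| 0.9 | 0.95 | 5% |

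If the covariate is fitted, as 10.4 hints, there is nothing further to gain.

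**The case against.** The strongest reply is that 10.4 leaves the fixed effects open and does not exclude these factors, since the mean structure is to be determined later. That is so: the fault is a missing commitment, not a decision to omit. The reply does not remove the point, because a mean structure chosen after exploratory analysis is what naming the design factors would avoid.

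Several limits stand.

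- **Baseline is not ignored.** It enters through the change score or as a covariate. A reader might compare the covariate with an analysis of follow-up dmfs alone and infer a saving of r². Section 10.2 sizes the trial on mean dmfs at follow-up, but 10.4 does not propose analysing it that way. The right comparator is the change score.
- **Standard errors.** A reader might infer that leaving out the strata gives standard errors that do not match the design, or intervals that are too wide. That argument needs stratification to have forced balance, and the final-digit rule does not. Under independent draws, a model with a center random effect and no strata already reflects chance imbalance in its standard error. What remains is precision, and correction of the imbalance that actually occurs.
- **Size of the gain.** Nothing in the documents says how much agency or class number explains. Zero is possible, and baseline dmfs may already absorb stable agency differences.
- **Number of clusters.** The calculation treats the 52 classrooms as clusters, whereas 5.3.1 randomises centers, some with 2-3 classes. There may be fewer clusters, so the cost in degrees of freedom may be somewhat higher.
- **Section 4 wording.** Class number can fairly be read as population size made operational. The real mismatch is the missing agency.

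**Conclusion.** The point holds as a cheap improvement to the pre-specified model. The strata of 5.3.1 are absent from 10.4, and the baseline covariate is described as custom without being committed to. Adding the strata changes power from 80% to between 79.8% and 87.8% at 14 children per cluster, for assumed shares of 0 to 50%. Using baseline as a covariate instead of a change score saves 5 to 25% of variance for assumed correlations of 0.9 to 0.5, and nothing if it is already fitted. The strata gain was computed for unadjusted dmfs, so the two may overlap and must not be summed.

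The documents do not support calling the planned analysis invalid or the trial underpowered for this reason. On the plan's own inputs, power for the 40% effect is about 98 to 99%. The precision matters if the true effect is smaller, and the correction for imbalance matters if the draws fall unevenly by agency or center size.

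**What to change.** In section 10.4, state that the primary model will include baseline dmfs, agency (5 levels) and class number (1 vs 2-3) as fixed effects and a random effect for Head Start Center, with a small-sample method for the degrees of freedom. Replace the permissive wording on the baseline covariate and the cluster effect with a commitment, and say how this model relates to the change from baseline that defines the outcome.

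In the Protocol Summary and section 4, name the same two strata as 5.3.1, including agency, and use one term for the randomised unit, since section 4 speaks of classrooms and 5.3.1 of centers.

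The cost is a few sentences, no new data, and about five cluster-level degrees of freedom. If the strata explain nothing, this loses about 0.2 points of power with 26 clusters per arm, or about 0.9 with 13.

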10.2 Sample Size Considerations

Sample size is based upon the following assumptions:

1. The primary outcome measure is dmfs, measured at baseline and annually for three years after the beginning of the intervention when the HS children ages 3-5 at enrollment (or possibly 6, depending on the timing of enrollment) will be ages 6-8 (or possibly 9).
2. The test statistic used is the t-test for 2 independent samples, with an inflation factor for the cluster randomized design.^{29, 30}
3. The null hypothesis is no difference in the mean dmfs between the 2 randomized groups 2 years and 3 years after the beginning of the intervention when the children are 5-7 6-8 (or possibly 9) years old. The alternative hypothesis is that there is a difference.
4. Type I error rate will be set at 0.05
5. Type II error rate will be set at 0.20 (Power = 0.80)
6. From the 1999 IHS oral health survey ⁵, the average dmfs for AI children ages 5-7 was 18.55. It was also observed that Navajo children tended to have dmfs measures about 30% higher than the national average for all AI children. Therefore, it was assumed that the average dmfs for Navajo children ages 5-7 will be about 24 under conditions of usual care, with a standard deviation of about 24. We also assumed a 40% reduction in this average dmfs measure for group 1.
7. Based on the experience of other studies the Centers for American Indian and Alaska Native Health have conducted with AI communities, a 70% retention rate was assumed.

8. If subjects drop out of the study due to adverse effects or other reasons, we will ask them to continue in the follow-up even if treatment is discontinued, so that we can perform an “intention to treat” analysis. The “intention to treat” analysis will be the primary analysis of the study.
9. We also assumed an average HS class size of about 20 children and an intraclass correlation of about 0.045, considered to be an appropriate intraclass correlation.³¹

On the basis of the assumptions above, we calculate a need to randomize 52 HSC classrooms, or about 26 HSC classrooms in group 1 and 26 HSC classrooms in group 2. This means that we will need to enroll about 1040 children, or 520 children in group 1 and 520 children in group 2. Sample size calculations are shown in the table in *Appendix B*.

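### The randomisation rule in 5.3.1 is an unrestricted 50:50 draw for each HSC, so stratifying does not deliver the balance the protocol says it ensures

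*Combined protocol and SAP*

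**What the plan says.** Section 5.3.1 forms strata from number of classes (1 versus 2-3) and the five Navajo agencies, which gives up to 10 strata. It states two aims. The first is overall balance: "This will be done to ensure approximately equal sample sizes in the intervention and control groups". The second is local: "approximately an equal number of intervention and control participants within each Navajo agency". The mechanism follows in the same paragraph: "if the random number ends with the digit 0-4, the HSC will be assigned to the control arm", with last digits 5-9 going to intervention.

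Section 4 makes the same promise for children: "This will make the number of children in each of the 2 arms of the study approximately equal". Section 10.2 plans "about 26 HSC classrooms in group 1 and 26 HSC classrooms in group 2".

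The unit is not the same throughout. Section 5.3.1 assigns HSCs. Section 4 says the study will "randomly assign the HSC classrooms to the 2 arms of the study within the strata", and section 10.2 also counts classrooms.

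On analysis, section 10.4 treats baseline as a covariate and says that clustering "can also be accounted for in the mixed model with a random effect for group". It leaves the mean structure open and names neither agency nor number of classes.

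**The concern.** Stratifying balances arms only when assignment inside each stratum is restricted, for example by a fixed split of a random ordering or by permuted blocks. A separate fair draw for each HSC is not a restriction. The stated aim therefore does not follow from the stated rule, and a programmer who codes 5.3.1 as written will produce simple randomisation of HSCs.

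Validity is not at stake: the allocation is still random, the comparison is unbiased and type I error is not inflated. At stake are the promised balance, some precision, and credibility. A reader told that the arms are balanced by agency and size may find that they are not, with no stratum term named in the primary model.

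**Working it through.** **Why the strata do nothing.** Under the digit rule every allocation of n HSCs has probability 0.5^n. Grouping the HSCs first does not change that probability, so the distribution of arm totals is the same as without strata.

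**Inputs.** From section 10.2: 52 classrooms planned 26:26, 20 children per class, 70% retention (14 retained), ICC 0.045, SD 24, difference 40% of 24 = 9.6, two-sided alpha 0.05. From section 5.3.1: five agencies, probability 0.5 per HSC. The number of HSCs is not given. I assume 30 to 52 HSCs holding 52 classrooms, and agencies of equal size.

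**The planned 26:26 split.** With 52 single units, the number in one arm is Binomial(52, 0.5):
- P(exactly 26:26) = C(52,26)/2^52 = 0.110
- P(30:22 or worse) = 0.332
- P(32:20 or worse) = 0.126

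**When HSCs hold one to three classes.** Exact convolution of the independent draws, 52 classrooms in total:

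| HSCs with 1 / 2 / 3 classes | Total HSCs | P(gap ≥ 8 classrooms) | P(gap ≥ 12 classrooms) |
|---|---|---|---|
| 36 / 8 / 0 | 44 | 0.398 | 0.183 |
| 24 / 14 / 0 | 38 | 0.437 | 0.220 |
| 12 / 14 / 4 | 30 | 0.497 | 0.284 |

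**Within agencies.** Let p be the chance that one agency of k HSCs has a gap of 4 or more. The chance that at least one of five does is 1 − (1 − p)^5:

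| k | p | Any of five |
|---|---|---|
| 6 | 0.219 | 0.709 |
| 7 | 0.125 | 0.487 |
| 8 | 0.289 | 0.818 |
| 9 | 0.180 | 0.629 |
| 10 | 0.344 | 0.878 |

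The figures alternate because an odd k cannot have a gap of exactly 4; the cut-off is then in effect 5.

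**Cost in precision.** The variance ratio at 20:32 against 26:26 is (1/20 + 1/32)/(2/26) = 0.08125/0.07692 = 1.056. Averaged over all possible draws, the variance rises by about 2% for 52 single units and by 3% to 4% for the three layouts above.

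**Cost in power** (normal approximation, effective n per arm = classrooms × 14 / design effect):
- Design effect 1 + 19 × 0.045 = 1.855: 97.7% at 26:26, 97.5% at 30:22, 97.1% at 32:20.
- Design effect 1 + 13 × 0.045 = 1.585: 99.0%, 98.9%, 98.6%.
- Starting from a true 80%: 79.1% at 30:22, 77.8% at 32:20.

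The first two lines lie above 80% because the stated inputs need only about 99 × 1.855 / 0.70 = 262 children per arm, not 520. That is a separate matter, and this point does not depend on it.

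**With restriction.** A near-1:1 split in each stratum limits the gap to 1 HSC per stratum, hence 2 per agency. I simulated this over 10 strata with 30 to 52 HSCs, 8,000 draws per assumed layout. With each odd HSC placed at random, a gap of 8 or more classrooms still had a chance of 0 to 16%, depending on how HSCs were spread over strata. With the odd HSCs placed to balance total classrooms, no draw reached 8 and the 95th percentile of the gap was 0 to 2.

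**The case against.** The strongest reply is that little follows from this. There is no bias, and power on the plan's own inputs moves by less than one percentage point; the fall from 80% to 77.8% would apply only if true power were 80%. That stands, and it limits how much weight the point can bear.

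The cut-offs are also mine, since the documents never define approximately equal. At a gap of 6 or more HSCs, the chance for at least one agency is 15%, 8%, 31%, 18% and 44% for 6 to 10 HSCs per agency. So the agency figures depend on the threshold as well as on the assumed counts. Under either threshold, balance within agency is left to chance.

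Section 4 says that the Manual of Procedures details randomization, and 5.3.1 says that a program will be developed. Either could contain a restriction that I cannot see. What can be said is that the protocol states none. If one exists, 5.3.1 misdescribes the method and still needs correcting.

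Section 4 has HSCs enrolling in each of two years, which could prevent a single ordered split. Sections 5.1 and 5.3.1, however, have HSCs selected and listed before randomisation, and the split could be made separately in each wave.

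Finally, if the draws really were unrestricted, validity does not require stratum terms in the model. That is correct. Their purpose then is precision, and protection against whatever imbalance has occurred.

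**Conclusion.** The concern holds. As written, 5.3.1 and section 4 claim a balance that the digit rule does not provide, overall or by agency. Splits of 30:22 or worse would occur about one time in three with 52 single units. A gap of 8 or more classrooms would occur 40% to 50% of the time if HSCs hold one to three classes. At least one agency would have a gap of 4 or more HSCs with a chance of 49% to 88%. These figures rest on assumed HSC counts (30 to 52 in total, 6 to 10 per equal-sized agency) and on there being no restriction in the Manual of Procedures. That the strata add no balance under this rule rests on none of the assumed counts. The consequence is lost balance, a small loss of precision and weaker face validity. The trial remains valid, so this is a correction worth making and not a threat to the result.

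**What to change.** - **Section 5.3.1.** Replace the digit rule. Within each of the 10 strata, put the HSCs in computer-generated random order and split them near 1:1. Assign the odd HSCs by a random choice among the allocations with the smallest difference in total classrooms. This last step is needed because the larger-size stratum mixes two- and three-class HSCs, so equal HSC counts do not guarantee equal classroom counts. If HSCs enter in two waves, apply the procedure to each wave.
- **Sections 4, 5.3.1 and 10.2.** State in the same words whether the HSC or the classroom is the unit of randomisation.
- **Section 10.4.** Include agency and number of classes as fixed effects in the primary model alongside baseline dmfs.
- **If allocation is already done.** Report the rule actually used and the realised split of HSCs, classrooms and children by stratum, and add the stratum terms.

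The cost is a few lines in the randomisation program, one or two sentences in each of 5.3.1 and 10.4, and 5 degrees of freedom (4 for agency, 1 for size). Where all HSCs to be allocated are listed beforehand, restricting the split does not make assignments more predictable.
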